5.6 Clinical Criteria for Early Trial Termination

Early trial termination will be the result of the criteria specified below:

- 1. Quality or quantity of data recording is inaccurate or incomplete
- 2. Poor adherence to protocol and regulatory requirements
- 3. Incidence or severity of adverse drug reaction in this or other studies indicates a potential health hazard to participants
- 4. Plans to modify or discontinue the development of the study drug

In the event of Merck decision to no longer supply study drug, adequate notification will be provided so that appropriate adjustments to participant treatment can be made.

6.0 TRIAL ASSESSMENTS AND PROCEDURES

6.1 Trial Procedures

- Study procedures and their timing are summarized in the Schedule of Activities (SoA), Section 2.3.
- Adherence to the study design requirements, including those specified in the SoA, is essential and required for study conduct.
- The investigator is responsible for ensuring that procedures are conducted by appropriately qualified (by education, training, and experience) staff.
- All screening evaluations must be completed and reviewed to confirm that potential participants meet all eligibility criteria

- Additional evaluations/testing may be deemed necessary by the investigator, the Sponsor and/or Merck for reasons related to participant safety. In some cases, such evaluation/testing may be potentially sensitive in nature (eg, HIV, Hepatitis C), and thus local regulations may require that additional informed consent be obtained from the participant. In these cases, such evaluations/testing will be performed in accordance with those regulations.
- Procedures conducted as part of the participant's routine clinical management (eg, blood count) and obtained before signing of ICF may be utilized for screening or baseline purposes provided the procedure met the protocol-specified criteria and were performed within the time frame defined in the SoA.
- All screening evaluations must be completed and reviewed to confirm that potential participants meet all eligibility criteria. The investigator will maintain a screening log to record details of all participants screened and to confirm eligibility or record reasons for screening failure, as applicable.

6.1.1 Administrative and General Procedures

6.1.1.1 Informed Consent

The Investigator must obtain documented consent from each potential participant or each participant's legally acceptable representative prior to participating in a clinical trial. If there are changes to a participant's status during the study (e.g. health requirements) the investigator or medically qualified designee must ensure appropriate documented informed consent is in place.

6.1.1.2 General Informed Consent

Informed consent must be documented by the participant's dated signature or by the participant's legally acceptable representative's dated signature on a consent form along with the dated signature of the person conducting the consent discussion.

A copy of the signed and dated consent form should be given to the participant (or their legally acceptable representative) before participation in the trial.

The initial informed consent form, any subsequent revised written informed consent form and any written information provided to the participant must receive the IRB/ERC's approval/favorable opinion in advance of use. The participant or his/her legally acceptable representative should be informed in a timely manner if new information becomes available that may be relevant to the participant's willingness to continue participation in the trial. The communication of this information will be provided and documented via a revised consent form or addendum to the original consent form that captures the participant's dated signature or by the participant's legally acceptable representative's dated signature.

Specifics about a trial and the trial population will be added to the consent form template at the protocol level.

Confidential

The informed consent will adhere to IRB/ERC requirements, applicable laws and regulations and Sponsor requirements.

If the investigator recommends continuation of study intervention beyond disease progression, the participant or his/her legally acceptable representative will be asked to sign consent.

6.1.1.3 Inclusion/Exclusion Criteria

All inclusion and exclusion criteria will be reviewed by the investigator or qualified designee to ensure that the participant qualifies for the trial.

6.1.1.4 Medical History

A medical history will be obtained by the investigator or qualified designee. Medical history will include all active conditions, and any condition diagnosed within the prior 10 years until the first dose of study treatment (C1D1) that are considered to be clinically significant by the Investigator. Details regarding the disease for which the participant has enrolled in this study will be recorded separately and not listed as medical history.

6.1.1.5 Prior and Concomitant Medications Review

6.1.1.5.1 Prior Medications

The investigator or qualified designee will review prior medication use, including any protocolspecified washout requirement, and record prior medication taken by the participant within 28 days before starting the trial. Treatment for the disease for which the participant has enrolled in this study will be recorded separately and not listed as a prior medication.

6.1.1.5.2 Concomitant Medications

The investigator or qualified designee will record medication, if any, taken by the participant during the trial. All medications related to reportable SAEs and ECIs should be recorded as defined in Section 6.2.

6.1.1.6 Disease Details and Treatments

6.1.1.6.1 Disease Details

The investigator or qualified designee will obtain prior and current details regarding disease status.

6.1.1.6.2 **Prior Treatment Details**

The investigator or qualified designee will review all prior cancer treatments including systemic treatments, radiation and surgeries.

6.1.1.6.3 Subsequent Anti-Cancer Therapy Status

The investigator or qualified designee will review all new anti-neoplastic therapy initiated after the last dose of trial treatment. If a participant initiates a new anti-cancer therapy within 30 days after the last dose of trial treatment, the 30-day Safety Follow-up visit must occur before the first dose of the new therapy. Once new anti-cancer therapy has been initiated the participant will move into survival follow-up.

6.1.1.7 Assignment of Screening Number

All consented participants will be given a unique screening number that will be used to identify the participant for all procedures that occur. Each participant will be assigned only one screening number. Screening numbers must not be re-used for different participants.

6.1.2 Clinical Procedures/Assessments

6.1.2.1 Adverse Event (AE) Monitoring

The investigator or qualified designee will assess each participant to evaluate for potential new or worsening AEs as specified in the Trial Flow Chart and more frequently if clinically indicated. Adverse experiences will be graded and recorded throughout the study and during the follow-up period according to NCI CTCAE Version 5.0 (see Appendix 5). Toxicities will be characterized in terms regarding seriousness, causality, toxicity grading, and action taken with regard to trial treatment.

Please refer to section 6.2 for detailed information regarding the assessment and recording of AEs.

6.1.2.2 Physical Exam

A complete physical examination will be conducted by an investigator or medically qualified designee (consistent with local requirements) as per institutional standard. Height and weight will also be measured and recorded.

A brief directed physical examination will be conducted by an investigator or medically qualified designee (consistent with local requirements) per institutional standard [specify if there are specific assessments that must be conducted as a minimum].

Investigators should pay special attention to clinical signs related to previous serious illnesses.

6.1.2.3 Full Physical Exam

The investigator or qualified designee will perform a complete physical exam during the screening period. Clinically significant abnormal findings should be recorded as medical history. The time points for full physical exams are described in Section 2.3. After the first dose of study intervention, new clinically significant abnormal findings should be recorded as AEs.

Investigators should pay special attention to clinical signs related to previous serious illnesses.

6.1.2.4 Directed Physical Exam

For cycles that do not require a full physical exam per the Section 2.3, the investigator or qualified designee will perform a directed physical exam as clinically indicated prior to study intervention administration. New clinically significant abnormal findings should be recorded as AEs.

Investigators should pay special attention to clinical signs related to previous serious illnesses.

6.1.2.5 Vital Signs

The investigator or qualified designee will take vital signs at screening, prior to the administration of each dose of trial treatment and at treatment discontinuation as specified in the Schedule of Activities (Section 2.3). Vital signs should include temperature, pulse, respiratory rate, weight and blood pressure. Height will be measured at screening only.

6.1.2.6 Eastern Cooperative Oncology Group (ECOG) Performance Scale

The investigator or qualified designee will assess ECOG status (see Appendix 1) at screening, prior to the administration of each dose of trial treatment and discontinuation of trial treatment as specified in the Schedule of Activities (Section 2.3).

6.1.2.7 Electrocardiograms and ECHO or MUGA

12-lead ECG will be obtained and reviewed by an investigator or medically qualified designee (consistent with local requirements) as outlined in the SoA using an ECG machine that automatically calculates the HR and measures PR, QRS, QT, and QTc intervals.

A MUGA scan (using technetium-based tracer) or an echocardiogram will be performed to assess LVEF as designated in the SoA. MUGA or echocardiogram scans should be performed locally in accordance with the institution's standard practice. MUGA scans are the preferred modality; however, whichever modality is used for an individual participant at baseline should be repeated for all subsequent LVEF assessments for that participant. LVEFs as assessed by the institution will be entered onto the CRF. Investigator assessment will be based upon institutional reports.

6.1.3 Clinical Safety Laboratory Assessments

Refer to Appendix 2 for the list of clinical laboratory tests to be performed and to the SoA for the timing and frequency.

• The investigator or medically qualified designee (consistent with local requirements) must review the laboratory report, document this review, and record any clinically relevant changes occurring during the study in the AE section of the CRF. The laboratory reports must be filed

with the source documents. Clinically significant abnormal laboratory findings are those which are not associated with the underlying disease, unless judged by the investigator to be more severe than expected for the participant's condition.

- All protocol-required laboratory assessments, as defined in Appendix 2, must be conducted in accordance with the laboratory manual and the SoA.
- If laboratory values from non-protocol-specified laboratory assessments performed at the institution's local laboratory require a change in study participant management or are considered clinically significant by the investigator (e.g., SAE or AE or dose modification), then the results must be recorded in the appropriate CRF (e.g., SLAB).
- For any laboratory tests with values considered clinically significantly abnormal during participation in the study or within 30 days after the last dose of study intervention, every attempt should be made to perform repeat assessments until the values return to normal or baseline or if a new baseline is established as determined by the investigator.

Details regarding specific laboratory procedures/assessments to be performed in this study are provided below. The total amount of blood/tissue to be drawn/collected over the course of the study (from prestudy to poststudy visits), including approximate blood/tissue volumes drawn/collected by visit and by sample type per participant can be found in the Lab Manual. Refer to the SoA (Section 2.3) for the timing of laboratory assessments.

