3.2 Secondary Objective(s), Hypothesis(es), and Endpoint(s)

(1) **Objective**: To evaluate the objective response rate resulting from treatment with Lenvatinib + pembrolizumab.

Hypothesis: Treatment with Lenvatinib + pembrolizumab will result in an improved objective response rate as compared with previously reported therapies including pembrolizumab monotherapy, ipilimumab + nivolumab and tebentafusp.

Secondary Endpoint: Objective response rate (complete and partial responses assessed by iRECIST)

(2) **Objective**: To evaluate the effect of treatment with Lenvatinib + pembrolizumab on overall survival.

Hypothesis: Treatment with Lenvatinib + pembrolizumab will result in improved overall survival as compared with previously reported therapies including pembrolizumab monotherapy, ipilimumab + nivolumab and tebentafusp.

Secondary Endpoint: Overall survival, defined as the time from enrollment to death (resulting from any cause).

(3) **Objective**: To evaluate the safety and tolerability of treatment with Lenvatinib + pembrolizumab in patients with metastatic uveal melanoma.

Hypothesis: Treatment with Lenvatinib + pembrolizumab will demonstrate an acceptable toxicity profile in patients with metastatic uveal melanoma.

Secondary Endpoint:

• Adverse events (per CTCAE v5.0)

• Frequency of treatment interruption, dose reduction, and treatment discontinuation due to treatment related adverse events (TRAE).

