- 9. Paired fresh tumor biopsy specimens (to be collected pre- treatment and cycle 3 day 8) will be collected for at least 15 patients (in no certain order) who consent. Subjects with tumor metastases that are not amenable to image guided biopsies or who have a contraindication to biopsy (including but not limited to anticoagulation therapy that cannot be interrupted for a biopsy) are still eligible for participation in the clinical trial without undergoing biopsies. Archival tissue may be used in place of pre-treatment biopsy.

System	Laboratory Value			
Hematological				
Absolute neutrophil count (ANC)	≥1500/µL			
Platelets	≥100 000/µL			
Hemoglobin	\geq 9.0 g/dL or \geq 5.6 mmol/L ^a			
Renal				
Creatinine OR Measured or calculated ^b creatinine clearance (GFR can also be used in place of creatinine or CrCl)	$\leq 1.5 \times \text{ULN } \underline{\text{OR}}$ $\geq 30 \text{ mL/min for participant with creatinine levels}$ $> 1.5 \times \text{institutional ULN}$			
Hepatic				
Total bilirubin	\leq 1.5 ×ULN OR direct bilirubin \leq ULN for participants with total bilirubin levels >1.5 × ULN (patients with clinical evidence of Gilbert's syndrome and elevated bilirubin are eligible for participation).			
AST (SGOT) and ALT (SGPT)	\leq 2.5 × ULN (\leq 5 × ULN for participants with liver metastases)			

Table 2 Adequate Organ Function Laboratory Values

Coagulation					
International normalized ratio (INR) OR prothrombin time (PT) Activated partial thromboplastin time (aPTT)	\leq 1.5 × ULN unless participant is receiving anticoagulant therapy as long as PT or aPTT is within therapeutic range of intended use of anticoagulants				
ALT (SGPT)=alanine aminotransferase (serum glutamic pyruvic transaminase); AST (SGOT)=aspartate aminotransferase (serum glutamic oxaloacetic transaminase); GFR=glomerular filtration rate; ULN=upper limit of normal.					
^a Criteria must be met without erythropoietin dependency and without packed red blood cell (pRBC) transfusion within last 2 weeks.					
^b Creatinine clearance (CrCl) should be calculated per	institutional standard.				
Note: This table includes eligibility-defining laboratory value requirements for treatment; laboratory value requirements should be adapted according to local regulations and guidelines for the administration of specific chemotherapies.					

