Based on the known toxicity profiles of pembrolizumab and lenvatinib, certain treatment-related AEs are uniquely associated with one drug versus the other. For example, hypertension, arterial thrombotic events, proteinuria, and hemorrhagic events are known risks for lenvatinib treatment, while immune-related AEs are risks for pembrolizumab treatment. However, certain AEs, such as such as diarrhea, hypothyroidism, and liver enzyme elevation, may be initially considered attributable to either study drug. Therefore, evaluation of attribution is important for determining the study drug most likely related to the AE, or an alternative etiology, and subsequently proper clinical management. The following aspects should be considered:

1. Timing of AE onset

Since lenvatinib is dosed daily and continuously due to a relatively short half-life (28 hours), and pembrolizumab is dosed Q3W due to a long half-life, lenvatinib can be interrupted to assess whether an AE improves/resolves with dechallenge (ie, interruption of treatment) based on the following two scenarios:

- If an AE is identified during a treatment cycle (ie, between 2 pembrolizumab doses), only lenvatinib dose interruption is needed.
- If an AE is identified at the beginning of a treatment cycle, lenvatinib can be interrupted and dosing of pembrolizumab should be held.

If the subject recovers from an AE in response to lenvatinib interruption (ie, positive dechallenge), the event is more likely to be related to lenvatinib. Otherwise, after excluding other alternative explanations, an immune-related AE should be considered.

2. Severity of AE

If an AE is suspected to be treatment related and is severe/life threatening at the time of onset or is rapidly worsened, action including interrupting both drugs and initiating treatment with a corticosteroid (with exception of hypothyroidism, TIDM) and other supportive care should be taken promptly.

- 3. Participants receiving the combination therapy (pembrolizumab + lenvatinib) must discontinue study therapy if any of the following occur:
 - ALT or AST >5 X ULN for more than 2 weeks. Pembrolizumab will have already been permanently discontinued per Table 6,[X], but

Confidential
lenvatinib may be administered at a reduced dose by the time this criterion is met and must be permanently discontinued immediately.

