10.1.1 Definition of AE

AE definition

- An AE is any untoward medical occurrence in a clinical study participant, temporally associated with the use of study intervention, whether or not considered related to the study intervention.
- NOTE: An AE can therefore be any unfavorable and unintended sign (including an abnormal laboratory finding), symptom, or disease (new or exacerbated) temporally associated with the use of a study intervention.
- NOTE: For purposes of AE definition, study intervention (also referred to as Merck product) includes any pharmaceutical product, biological product, vaccine, diagnostic agent, or protocol specified procedure whether investigational or marketed (including active comparator product, or run-in intervention), manufactured by, licensed by, provided by, or distributed by Merck for human use in this study.

Events meeting the AE definition

- Any abnormal laboratory test results (hematology, clinical chemistry, or urinalysis) or other safety assessments (eg, ECG, radiological scans, vital signs measurements), including those that worsen from baseline, considered clinically significant in the medical and scientific judgment of the investigator.
- Exacerbation of a chronic or intermittent pre-existing condition including either an increase in frequency and/or intensity of the condition.
- New conditions detected or diagnosed after study intervention administration even though it may have been present before the start of the study.
- Signs, symptoms, or the clinical sequelae of a suspected drug-drug interaction.
- Signs, symptoms, or the clinical sequelae of a suspected overdose of either study intervention or a concomitant medication.
- For all reports of overdose (whether accidental or intentional) with an associated AE, the AE term should reflect the clinical symptoms or abnormal test result. An overdose without any associated clinical symptoms or abnormal laboratory results is reported using the terminology "accidental or intentional overdose without adverse effect."

Events NOT meeting the AE definition

- Medical or surgical procedure (eg, endoscopy, appendectomy): the condition that leads to the procedure is the AE.
- Situations in which an untoward medical occurrence did not occur (social and/or convenience admission to a hospital).
- Anticipated day-to-day fluctuations of pre-existing disease(s) or condition(s) present or detected at the start of the study that do not worsen.

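### Hepatic laboratory toxicity can be under-captured in the safety endpoint when it is attributed to liver metastases, and no laboratory summary is planned to offset this

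*Combined protocol and SAP*

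**What the plan says.** **Endpoint.** Section 3.2(3) has two safety components. The first is adverse events graded by CTCAE v5.0. The second is the frequency of interruption, dose reduction and discontinuation due to treatment-related AEs. The stated hypothesis is an acceptable toxicity profile.

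**From laboratory report to AE.** Section 6.1.3 asks the investigator or designee to "record any clinically relevant changes occurring during the study in the AE section of the CRF". It then defines the term: "Clinically significant abnormal laboratory findings are those which are not associated with the underlying disease". The sentence goes on to make an exception for a finding that the investigator considers worse than that patient's disease would explain. In Appendix 5, section 10.1.1 counts an abnormal laboratory result as an AE if it is "considered clinically significant in the medical and scientific judgment of the investigator". The same section defines an AE irrespective of its relation to study treatment, and it excludes progression of the disease under study.

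**Population and drugs.** Table 2 in 5.1.1 limits AST and ALT to 2.5 × ULN at entry but allows up to 5 × "ULN for participants with liver metastases". The overlapping-toxicities text (section 5.2.2 in the table of contents) says that "diarrhea, hypothyroidism, and liver enzyme elevation, may be initially considered attributable to either study drug".

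**Value-based hepatic rules.** Section 6.2.6 item 3 makes AST or ALT ≥3 × ULN, with total bilirubin ≥2 × ULN and ALP <2 × ULN, an event of clinical interest (ECI) that must be reported to the drug supplier. Item 3 of the overlapping-toxicities text requires discontinuation for ALT or AST >5 × ULN lasting more than 2 weeks, or for ALT or AST >3 × ULN with bilirubin >2 × ULN or INR >1.5.

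**Data and analysis.** "The laboratory reports must be filed" with the source documents (6.1.3). Section 7 covers response rate, progression-free survival and futility. It describes no safety or laboratory analysis.

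**The concern.** The definition of an AE is independent of cause, but in 6.1.3 a judgement about cause is made before an AE exists. A laboratory abnormality put down to the tumour, and not thought worse than expected, is not clinically significant under 6.1.3 and so need not become an AE. The definition's neutrality about cause never comes into play.

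This matters most for the liver. The protocol expects some patients to have hepatic metastases and raised transaminases at entry, and it recognises both drugs as possible causes of a further rise. Disease is then a ready explanation for an event that may be drug-related. If such events are left out of the AE record and no laboratory table is produced, a reader of the safety results cannot see them or judge the attribution. A conclusion of acceptable toxicity would rest partly on that unseen step.

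**Working it through.** The plan states no figure for this point, so there is nothing to reproduce. The check sets the rules side by side.

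**1. What must be true for a hepatic value to miss the AE endpoint.** Under 6.1.3 two judgements are needed: the finding is associated with the underlying disease, and it is not more severe than expected. Both are made by the investigator, and the protocol gives no numeric limit for what is expected.

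**2. Which of these values another rule would pick up.** Take rises for which both judgements have been made.

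| Pattern | ECI (6.2.6 item 3)? | Item 3 stopping limit? |
|---|---|---|
| AST/ALT ≥3 × ULN, bilirubin ≥2 × ULN, ALP <2 × ULN | Yes | Yes, if AST/ALT >3 and bilirubin >2 × ULN |
| Same, but ALP ≥2 × ULN | No | Yes, if AST/ALT >3 and bilirubin >2 × ULN |
| AST/ALT ≥3 × ULN, bilirubin <2 × ULN | No | Only if >5 × ULN for more than 2 weeks, or >3 × ULN with INR >1.5 |
| Bilirubin >3 × ULN, AST/ALT <3 × ULN | No | No |

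The Table 4 footnotes place AST/ALT >5 × ULN and bilirubin >3 × ULN at Grade 3 when baseline is normal. An isolated Grade 3 rise can therefore fall outside the ECI.

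**3. Whether a forced stop restores the event.** The second component of 3.2(3) counts stops due to treatment-related AEs. A participant who meets an item 3 limit through a rise attributed to metastases stops both drugs, but the stop does not qualify for that component.

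**4. Whether an analysis restores it.** Section 7 plans no grading, shift table or ECI count. CRF entry is stated for clinically relevant changes, for certain results from tests outside the protocol, and for LVEF (6.1.2.7). It is not stated for every protocol-required laboratory value.

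**5. Why one grading scale is not enough.** With an abnormal baseline, the Table 4 footnotes grade AST/ALT relative to baseline. For a participant entering at 5 × ULN:
- Grade 2 starts above 3.0 × 5 = 15 × ULN.
- Grade 3 starts above 5.0 × 5 = 25 × ULN.

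The ECI and item 3 limits are multiples of ULN. Worst grade and threshold counts therefore give different views of the same patient.

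**6. Illustration of scale, on assumed inputs.** The documents give no hepatic event rate, no share of patients with liver metastases and no attribution rate. Assume x true events among N = 30 and a fraction f not recorded, so that recorded events = x(1 − f). Intervals are exact (Clopper-Pearson) 95%.

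| True events | f = 0 | f = 1/3 | f = 2/3 |
|---|---|---|---|
| 6 | 6/30 = 20% (8–39%) | 4/30 = 13% (4–31%) | 2/30 = 7% (1–22%) |
| 9 | 9/30 = 30% (15–49%) | 6/30 = 20% (8–39%) | 3/30 = 10% (2–27%) |
| 12 | 12/30 = 40% (23–59%) | 8/30 = 27% (12–46%) | 4/30 = 13% (4–31%) |

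These rows show only that a loss could be material in a trial of this size. They are not estimates.

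**The case against.** A reader might infer that disease-associated findings are barred outright and that a Grade 3 or 4 hepatic rise could appear nowhere in the safety data. The documents do not support that. The sentence in 6.1.3 goes on to its exception for findings more severe than expected. Section 10.1.1 also names results that worsen from baseline, where considered clinically significant, and exacerbations of pre-existing conditions. The ECI is triggered by values from scheduled or unscheduled tests, with no attribution step, and the item 3 limits also act on the numbers.

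A reader might also infer that hepatic toxicity *is* under-reported, or by how much. Nothing in the documents shows how investigators will attribute these rises. Nor can one assume that every value is in the database, since filing a report as source does not establish eCRF entry. Blood pressure, QTcF and LVEF are not laboratory findings under this clause, so the argument does not extend to them.

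Finally, investigator judgement of clinical significance is this protocol's chosen AE convention. In a single-arm pilot with no formal comparisons there is no second arm against which open-label reporting could differ.

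These objections narrow the point without removing it. The exception is a further judgement by the same investigator without a numeric limit. The ECI misses isolated rises and those with ALP ≥2 × ULN, and no summary of ECIs is planned. The stopping limits reach the endpoint only through a treatment-related attribution. Having no comparator removes differential reporting between arms, but an absolute rate can still be too low.

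**Conclusion.** The concern holds as a risk of under-capture. As written, 6.1.3 and 10.1.1 allow hepatic laboratory abnormalities in patients with liver metastases to stay out of 3.2(3) on the investigator's view that they are disease-related and no worse than expected. This applies mainly to isolated AST, ALT or bilirubin rises, and to rises with ALP ≥2 × ULN, that do not meet the ECI. Section 7 plans nothing to offset it.

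The direction of any effect on the recorded hepatic AE rate is downward. Its size cannot be known from the documents, because it depends on three quantities they do not give: the hepatic event rate, the proportion with liver metastases, and the share of rises attributed to disease. The point affects how the safety results can be read, and correcting it is a cheap improvement.

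**What to change.** 1. Keep investigator-reported AEs as they are.
2. State in 6.1.3 or 8.1 that all protocol-required hepatic laboratory values are entered in the eCRF.
3. Add to 3.2(3) and 7.2, for all treated participants and regardless of attribution, the worst post-baseline CTCAE v5.0 grade (with the baseline-abnormal convention) and baseline-to-worst shift tables for AST, ALT, ALP and bilirubin. Show these by presence of liver metastases.
4. Report the number of participants meeting each threshold already written in item 3 of the overlapping-toxicities text (5.2.2) and in 6.2.6 item 3.

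The tests are already scheduled, so no new procedures are needed. The cost is some added data entry, possibly with abstraction from filed reports, plus a few tables and a short addition to section 7. The raw hepatic rates will include some disease-driven rises and will look less favourable, so they should be shown beside the investigator-reported AEs. No dose or clinical management rule changes.
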